## **6. RESEARCH QUESTION AND OBJECTIVE**

The benefits of tiotropium bromide plus olodaterol FDC have been studied in controlled Phase III trials, however, data regarding quality of life and health status when treated with Spiolto® Respimat® in a real world setting is not available, especially in patients that have switched from previous monotherapy with tiotropium.

Due to the lack of real-world evidence data on LABA/LAMA combinations in Greece, this non-interventional study (NIS) plans a prospective analysis of COPD patients who switch from tiotropium monotherapy (Spiriva® Handihaler®) to dual therapy with tiotropium bromide plus olodaterol (Spiolto® Respimat®) in the Greek private and public sector pulmonary offices and clinics, and specifically to assess the change in the quality of life in relation to health status variations in this target population of COPD patients.

The results from this study will be used to scientifically support the improvement on the impact of COPD on the patient's health and quality of life after three months of dual therapy with tiotropium bromide plus olodaterol (Spiolto® Respimat®), as well as to understand how switch of therapy in COPD patients who initiated this dual therapy after using Spiriva® Handihaler® is approached by the Greek healthcare providers.

## **7. RESEARCH METHODS**

### **7.1 STUDY DESIGN**

This is a non-interventional, 3-months prospective, two visits, single-cohort, multicenter, nationwide study in patients with stable COPD who have been using maintenance therapy with tiotropium monotherapy (Spiriva® Handihaler®) for at least 3 months before, and for whom, according to their treating physician, a recent switch (within one week) to dual therapy with tiotropium bromide plus olodaterol (Spiolto® Respimat®) have been required, in the Greek private and public sector pulmonary offices and clinics.

In all cases, the decision to switch the treatment strategy from Spiriva® Handihaler® to Spiolto® Respimat® will be previous and completely independent from the initiation of this non-interventional study. Additionally, the decision of the treating physician will be according to the daily clinical practice in the corresponding centre.

[figure not shown]
The intended Health Care Professionals (HCPs) are office-based pulmonologists and practice physicians from Hospital pulmonary clinics, who are treating symptomatic COPD patients every day, being aware that most of their patients suffer from the physical restrictions induced by the disease per se.

Each investigator will recruit up to 10 eligible patients in a consecutive manner from those who come to control visits and have been using tiotropium administered with Spiriva® Handihaler® for at least 3 months before the decision to switch to a combination therapy

with tiotropium bromide plus olodaterol administered with Spiolto® Respimat® has been made. The enrolment period will last for a maximum of 6 months. All centers will stop recruitment once the total sample size of 1500 patients is achieved or, alternatively, at the end of the 6-months planned period of enrolment.

The study will collect data from two visits: baseline (within one week after the time of treatment switch) and approximately at 3 months ( $\pm 2$  weeks, according to clinical practice) (see Figure 1). In case of premature discontinuation of Spiolto® Respimat® for any reason (including treatment discontinuation, withdrawal of patient willingness to participate, or unexpected patient problems to continue with the study), an additional unscheduled visit will be performed, if possible according to clinical practice. In this visit, the specific reason for discontinuation will be assessed and all the effectiveness and quality of life variables will be collected as planned for the regular final visit at 3 months.

**Figure 1.** Study scheme

## 7.2 SETTING

It is planned that data of approximately 1500 COPD patients from approximately 150 sites (around 143 office-based pulmonologists and 2 Hospital pulmonary clinics) throughout Greece will be collected. Each investigator will recruit up to 10 eligible patients in a consecutive manner who have been using tiotropium administered with Spiriva® Handihaler® for at least 3 months before the decision to switch to a combination therapy with tiotropium bromide plus olodaterol administered with Spiolto® Respimat® has been made, according to the daily clinical practice in the corresponding site.

### 7.3 STUDY POPULATION

Approximately 1500 patients with chronic obstructive pulmonary disease (COPD) who have recently switched (within one week) from Spiriva® Handihaler® to Spiolto® Respimat® according to the daily clinical practice in the corresponding site, are to be observed by approximately 143 pulmonologists in the setting of private practice and 2 Hospital Pulmonary Clinics all over Greece. Hospital Pulmonary Clinics will act as coordinating sites of the study.

The NIS will take place in Greece and sites in urban as well as rural areas will be included. The nationwide distribution of the participating pulmonologists as well as the number of patients enrolled are intended to ensure that the data collected are representative.

**Inclusion criteria:**

1. Female and male patients  $\geq 40$  years of age
2. Patients diagnosed with COPD who have been using tiotropium administered with Spiriva® Handihaler® for at least 3 months before a recent switch (within last week) to a combination therapy with tiotropium bromide plus olodaterol administered with Spiolto® Respimat® has been made
3. Written informed consent prior to participation
4. Patient should be able to read, comprehend and complete study questionnaires

**Exclusion criteria:**

1. Patients with contraindications according to Spiolto® Respimat® SmPC
2. Patients who have been treated with inhaled corticosteroids (ICS) as maintenance therapy\* or with a LABA/LAMA combination (free or fixed dose) in the previous 6 weeks  
*\*Note: patients with temporary corticosteroids (CS) use during acute exacerbations in the previous 6 weeks can enter the study*
3. Patients who have been treated with Spiriva® Respimat®, with other LAMA different than Spiriva®, or with a combination of Spiriva®+LABA/ICS in the previous 6 weeks
4. Patients diagnosed with asthma or with asthma COPD overlap syndrome (ACO)
5. Patients for whom availability at the enrolling site during the planned study period of approximately 3 months is not possible
6. Pregnancy and lactation
7. Patients currently listed for lung transplantation
8. Current participation in any clinical trial or any other non-interventional study of a drug or device.
9. Patients who initiated the treatment with tiotropium bromide plus olodaterol older than 7 days before their enrolment in the present study.

### 7.4 STUDY VISITS

The enrolment period of the study will last for a maximum of 6 months. Enrolled patients will undergo two study visits: visit 1 (baseline visit) during screening and enrolment and visit 2 (follow up visit) 3 months ( $\pm 2$  weeks) after the baseline visit. Instead of the

regular visit 2 at 3-months, an unscheduled visit will take place in case of premature discontinuation to assess the specific reason for discontinuation, to complete main data collection parameters and to check for compliance and safety issues.

Visit windowing will be performed as described in Table 7.4:1, in order to assign data to the relevant study visit based on the actual day of the assessment. However, in the listings, all visits performed will be displayed (even if outside time-window).

[figure not shown]
Table 7.4:1 Analysis Visit Window

Analysis visits	Target Day	Analysis visit window [days]
Baseline	1	<=1
3 Months	92	63-121

Safety data are excluded from analysis visit mapping window and the investigator may enter data as needed.

Post baseline: Any assessment after the baseline visit.

## 8. VARIABLES

***COPD history and clinical characteristics at baseline and changes up to 3-months visit:***

- Months since COPD diagnosis, defined as: (Date at enrolment – Date of diagnosis)/30.5
- Gold group (A, B, C, D)

- COPD type (Chronic, bronchitis, Emphysema, Other)
- Number of exacerbations in the year before baseline (None, 1, 2, >2)
- Number of hospitalizations in the year before baseline (None, 1, 2, >2)
- Smoking Status (Never, Past, Current, Unknown)
- Packyears
- Presence of Eosinophilia (Yes, No)
- Months since PFTs performed, defined as: (Date of enrolment-Date of PFTS performed)/30.5
- FEV1/FVC % predicted ratio
- FEV1% predicted.

***Respiratory comorbidities and allergies at baseline and changes up to 3-months visit:***

- Pneumonia (Yes, No, Not evaluated)
- Allergic rhinitis (Yes, No, Not evaluated)
- Bronchiectasis (Yes, No, Not evaluated)
- Lung diseases due to external agents (Yes, No, Not evaluated)

***Comorbidities:***

- Diabetes mellitus (Yes, No, Unknown)
- Osteoporosis (Yes, No, Unknown)
- Cardiovascular diseases (Yes, No, Unknown) (including heart failure, atrial fibrillation and other arrhythmias)
- Malignancies (Yes, No, Unknown)
- Anxiety/depression (Yes, No, Unknown)
- Insomnia (Yes, No, Unknown)
- Pulmonary artery hypertension (Yes, No, Unknown)
- Sleep apnea (Yes, No, Unknown)
- Gastroesophageal reflux disease (Yes, No, Unknown)
- Hemolytic anemia (Yes, No, Unknown)

- Atopy (Yes, No, Unknown)
- Sinusitis (Yes, No, Unknown)
- Emphysema (Yes, No, Unknown)
- Duration of each Comorbidity(months) is defined as: (Stop Date/ICF Date- Start Date)/30.5

***Current and past COPD therapies*** (in the period of one year before enrolment)

- Short Acting  $\beta$ 2-agonists (Yes, No)
- Long Acting  $\beta$ 2-agonists (LABA) (Yes, No)
- Short Acting anticholinergics (Yes, No)
- Short Acting anticholinergics (LAMA) (Yes, No)
- Inhaled corticosteroids (ICS) (Yes, No)
- PDE4 inhibitors (Yes, No)
- Methylxanthines (Yes, No)
- LABA/ICS Combinations (Yes, No)
- LAMA/LABA Combinations (Yes, No)
- Duration of treatment (months) defined as: (Stop Date-Start Date)/30.5

***Relevant concomitant medications at baseline and changes up to 3-months visit:***

- Use of concomitant inhalers (Yes, No)
- Other concomitant medications

[REDACTED]

***COPD Assessment Test (CAT):*** patient-completed questionnaire assessing globally the impact of COPD (cough, sputum, dysnea, chest tightness) on health status. It is a unidimensional score based on 8 items each of them scaling from 0 to 5. Range of CAT scores from 0–40. Higher scores denote a more severe impact of COPD on a patient's life. The difference between stable and exacerbation patients is five units. No target score represents the best achievable outcome, however, CAT scores <10 corresponding to mild impact on patient's life are usually considered those representing patients without impaired health status

**EQ-5D-5L questionnaire**: a well-established and commonly used tool for the measurement of patients QoL. The EQ-5D-5L consists of two parts: the EQ-5D descriptive system and the EQ visual analogue scale (EQ VAS). The EQ-5D-5L descriptive system comprises five dimensions (mobility, self-care, usual activities, pain/discomfort and anxiety/depression). Each dimension has five levels (no problems, slight problems, moderate problems, severe problems and extreme problems) was self-reported by the patient. The patient's decision results into a 1-digit number that expresses the level selected for that dimension. The digits for the five dimensions can be combined into a 5-digit number that describes the patient's health state. The EQ VAS records the patient's self-rated health on a vertical visual analogue scale where the endpoints are labelled 'best imaginable health state' and 'worst imaginable health state'. The VAS can be used as a quantitative measure of health outcome that reflects the patient's own judgement.

**Simplified medication adherence questionnaire (SMAQ)**: a short and simple questionnaire based on questions posed directly to the patient regarding his/her medication-taking habits, which was originally validated for the measurement of adherence in patients on anti-retroviral treatment. The aim is to assess whether the patient adopts correct attitudes in relation to the treatment for his disease. It is assumed that if the attitudes are incorrect, the patient is not compliant. It has the advantage that it provides information about the causes of non-compliance. The patient is considered as compliant if all questions are answered correctly.

SMAQ questionnaire is dichotomic (yes, no), any answer in the sense of non-adherent groups, assigns patient to the non-adherent category. Thus, patient is considered non-adherent if at least one answer to the SMAQ questionnaire is the following:

- 1: YES.
- 2: No
- 3: YES
- 4: YES
- 5: C, D or E
- 6: more than two days.

**Modified British Medical Research Council (mMRC) Dyspnea Scale**: it quantifies disability attributable to breathlessness and is useful for characterizing baseline dyspnea in patients with respiratory diseases, especially COPD. It consists of a five-level rating scale based on the patient's perception of dyspnea in daily activities.

**Patient Satisfaction and Preference**: will be measured with the part 1 of the abbreviated Patient Satisfaction Questionnaire (PASAPQ). The patient preference Spiriva® Handihaler® vs Spiolto® Respimat® is measured using PASAPQ (part 2).

***Adverse drug reactions (ADRs), fatal adverse events (AEs) and pregnancies.***

## **8.1 Exposures**

All included patients will be already receiving LAMA/LABA combination treatment with Spiolto® Respimat® after a recent switch (within one week) from previous maintenance therapy with tiotropium monotherapy (Spiriva® Handihaler®), according to the Greek SmPC.

The same group of patients at two different time-points (three-months ahead) will be considered for the comparison analyses: within one week after the switch of COPD treatment from tiotropium monotherapy (Spiriva® Handihaler®) to dual therapy with tiotropium bromide plus olodaterol (Spiolto® Respimat®) and three-months after the baseline visit. However, no minimal exposure will be required. Subjects with premature drug discontinuation for any reason will not be excluded from the analysis.

Spiolto® Respimat® contains:

- The long-acting anticholinergic tiotropium bromide. The dose dispensed is 2.5 micrograms of tiotropium per puff, equivalent to 3.124 micrograms tiotropium bromide monohydrate. The dose dispensed is the quantity available to patients after crossing the mouthpiece.
- The selective beta2-adrenoceptor agonist olodaterol. The dose dispensed is 2.5 micrograms of olodaterol per puff (as olodaterol hydrochloride). The dose dispensed is the quantity available to patients after crossing the mouthpiece.

The recommended daily dose of Spiolto® Respimat® for adults is 5 micrograms of tiotropium ion (tiotropium) plus 5 micrograms of olodaterol, equivalent to inhaling 2 puffs from the Respimat® inhaler once daily at the same time of day.

## **8.2 Outcomes**

### **8.2.1 Primary outcomes**

[figure not shown]
The primary outcome of this NIS will be the mean change in patients' quality of life (QoL) according to the total score of COPD Assessment Test (CAT) within three months after the switch from Spiriva® Handihaler® to Spiolto® Respimat® according to the daily clinical practice.

### **8.2.2 Secondary outcomes**

The secondary outcomes of the current study include:

- Change in the proportion of patients with COPD Assessment Test (CAT)  $\geq 10$  (representing impaired health status) within three months after the switch

- Mean change from baseline in the total EQ VAS within three- months after the switch
- Proportion of patients that change (improve/worsen) each of the 5 dimensions of the EQ-5D-5L within three-months after the switch
- Rate of adherence to medication of COPD patients according to the SMAQ three-months after the switch.
- Mean total score in abbreviated PASAPQ (first 13 questions of Part 1) (patient satisfaction with the inhaler device) approximately three-months after the switch.
- Mean score of overall satisfaction according to Question 14 of PASAPQ (Part 1) three-months after the switch.
- Proportion of preference (Spiriva® Handihaler® vs Spiolto® Respimat®) according to PASAPQ (Part 2) three-months after the switch
- Mean score of willingness to continue with inhaler (Spiolto® Respimat®) according to PASAPQ (Part 2) three-months after the switch.
- Mean change of patients' dyspnea status according to the mMRC scale within three-months after the switch.

### 8.3 Covariates

The following variables will be considered, among others, as covariates and will be examined in terms of their association with the primary outcome measure.

- Patient' s age at baseline (<65 years,  $\geq 65$  years)
- Sex (female, male)
- Obesity (i.e. BMI  $\geq 30$  kg/m^2) (yes, no)
- Smoking habits (current smoker, past smoker).
- Packyears
- Gold group (A, B, C and D).

## 9. DATA SOURCES

Patient [REDACTED] records (paper and/or electronically) and patient reported outcomes from COPD patients as documented by the treating physician in his/her daily practice will be used as data source.

All participating physicians will be obliged to make a note of the patient's participation in the NIS in the patient 's medical records.

In the event of possible queries, the participating physician must be able to identify the patient observed. Medical information on the patient must be communicated and analyzed only using the patient number.

During this study, the following must be completed: To be completed by the physician:

- [REDACTED] (only at Visit 1)
- Patient medical files (including comorbidities and concomitant medications)
- Assessment of inhaler handling in daily use (only at Visit 2)

To be completed by the patient at Visit 1 (baseline) and Visit 2 (3-months visit):

- COPD Assessment Test (CAT)
- EQ-5D-5L questionnaire
- Modified Medical Research Council (mMRC) questionnaire

To be completed by the patient only at Visit 2 (3-months visit):

- Simplified Medication Adherence Questionnaire (SMAQ)
- Abbreviated Patient Satisfaction Questionnaire (PASAPQ)

## **10. DATA MANAGEMENT AND SOFTWARE/TOOLS**

A data management and review plan (DMRP) was created to describe all functions, processes, and specifications for data collection, cleaning, and validation. The electronic Case Report Forms (eCRFs) include programmable edits to obtain immediate feedback if data are missing (also negative answers, unknown), out of range, illogical or potentially erroneous. These rules may encompass simple checks such as range validation or presence/absence of data. Concurrent manual data review may be performed based on parameters dictated by the DMRP. Ad hoc queries to the sites may be generated and followed up for resolution. A source data quality audit may be initiated to ensure that the data in the database is accurate. Source data verification (SDV) will be performed at sites identified by a risk-based approach as needed.

The database will be housed in a physically and logically secure computer system maintained in accordance with a written security policy. The system will meet all current legal requirements regarding electronic study data handling. Patient confidentiality will be strictly maintained.

### **10.1 Software/Tools**

Stata V13.0 and R V4.0.2 will be used for the entire analysis.

### **10.2 Handling of Missing Values**

If missingness is more than 25% for a specific outcome [REDACTED] methodologies will be examined. More specific information is provided in Section

11.3.1

### 10.3 Handling of Inconsistencies in Data and Outliers

To identify the possible outliers, Z-score and IQR (interquartile range) methods will be used. An observation will be considered as an outlier if it is not included in the following interval for the primary and secondary continuous variables: ( $Q_1 - 1.5 \times IQR$ ,  $Q_3 + 1.5 \times IQR$ ). In order to visualise the outliers, histograms and/or scatterplots will be generated with the rest of the data. If the effect of the outliers is strong, delete or replace will be examined.

Any removal or replace at the analysis will be documented, stating the site and patient number as well as the reason for removal.

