### **5. AMENDMENTS AND UPDATES**

#### **5.1 Changes from protocol analysis**

Additional modifications from the CTP made in this SEAP:

- It was stated in CTP to exclude patients with missing values. Missing values will be treated in a different way according to their nature. Missing values due to Intercurrent Event (IE) are taken care at the estimands definitions, on the other hand, missing values not related to IE will be multiple imputed if missingness is greater than 25% for a specific variable.
- It was suggested in the CTP, [REDACTED]  
[REDACTED]
- To assess the potential associations between patient characteristics, treatment, preference [REDACTED]ing

to health status assessed with CAT will not be assessed via univariate methods, however the applicable [REDACTED] are included to the statistical models in the primary and the first secondary endpoint analysis.

[REDACTED]

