#### 11.2.1 Analysis of primary outcome.

11.2.1.1 Mean change in patients' quality of life (QoL) according to the total score of COPD Assessment Test (CAT) within three months after the switch from Spiriva® Handihaler® to Spiolto® Respimat®.

The primary estimand is defined as follows:

- A. Population: Is defined through inclusion/exclusion criteria of the study protocol to reflect the target population.
- B. Variable: Continuous variable response.

- C. Intercurrent Event (IE): Include death, drop-out due to any adverse event (AE) and treatment discontinuation. For patients experiencing an IE, the most extreme unfavourable value will be assigned (CAT score at 3 Months equals to 40).
- D. Population level summary: The change from Baseline of total CAT score within 3 Months.

Mixed model for repeated measurements (MMRM) assuming random missingness will be fitted. The dependent variable will be the CAT score at each visit. Visit, GOLD group, smoking habits, packyears, sex, age, and comorbidities appearing at a rate greater than 5% will be entered as covariates. Patients will be fitted at random and an unstructured covariance matrix will be used, allowing adjustment for correlations between study visits within the study patients. The Kenward- Roger degrees of freedom approximation will be used in the model (ddfm=kr).

Summaries of the estimated mean change from baseline of CAT score at 3 Months will be provided with 95% confidence interval. Model information will be provided as footnote under the corresponding table.

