#### **11.2.2.2 Mean change from baseline in the total EQ VAS within three- months after the switch**

Estimand:

- A. Population: Is defined through inclusion/exclusion criteria of the study protocol to reflect the target population.
- B. Variable: Continuous variable response.

C. Intercurrent Event (IE): Include death, drop-out due to any adverse event (AE) and treatment discontinuation. For patients experiencing an IE, the most extreme unfavourable value will be assigned (EQ-VAS equals to 0).

D. Population level summary: The change from Baseline of EQ-VAS score within 3 Months.

This endpoint will be analysed with a Mixed Model for Repeated Measures (MMRM) with EQ-VAS score as dependent variable. Visit, GOLD group, smoking habits, packyears, sex, age, and comorbidities appearing at a rate greater than 5% will be entered as covariates. Patients will be fitted at random and an unstructured covariance matrix will be used, allowing adjustment for correlations between study visits within the study patients. The Kenward- Roger degrees of freedom approximation will be used in the model (ddfm=kr).

Summaries of the estimated mean change from baseline of EQ-VAS score at 3 Months will be provided with 95% confidence interval. Model information will be provided as footnote under the corresponding table

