#### 11.2.2.4 Rate of adherence to medication of COPD patients according to the SMAQ three-months after the switch

Estimand:

A. Population: Is defined through inclusion/exclusion criteria of the study protocol to reflect the target population.

B. Variable: Binary variable response.

C. Intercurrent Event (IE): Include death, drop-out due to any adverse event (AE) and treatment discontinuation. For patients experiencing an IE, the most extreme unfavourable value will be assigned (Patient not adhered).

D. Population level summary: Proportion of adhered and not adhered patients.

For this endpoint frequency tables will be provided.

**11.2.2.5 Mean total score in abbreviated Q (first 13 questions of Part 1) (patient satisfaction with the inhaler device) approximately three-months after the switch**

Estimand:

A. Population: Is defined through inclusion/exclusion criteria of the study protocol to reflect the target population.

B. Variable: Continuous variable response.

C. Intercurrent Event (IE): Include death, drop-out due to any adverse event (AE) and treatment discontinuation. For patients experiencing an IE, the most extreme unfavourable value will be assigned (Total score equals to 13).

D. Population level summary: Mean total score of abbreviated Questionnaire three months after the switch

For this endpoint summary statistics tables will be provided.

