**11.2.2.6 Mean score of overall satisfaction according to Question 14 of PASAPQ (Part 1) three-months after the switch.**

Estimand:

A. Population: Is defined through inclusion/exclusion criteria of the study protocol to reflect the target population.

B. Variable: Continuous variable response.

C. Intercurrent Event (IE): Include death, drop-out due to any adverse event (AE) and treatment discontinuation. For patients experiencing an IE, the most extreme unfavourable value will be assigned (Score of Question 14 equals to 1)

D. Population level summary: Mean score of overall satisfaction three months after the switch.

Estimand will be assessed by summary statistics.

**11.2.2.7 Proportion of preference (Spiriva® Handihaler® vs Spiolto® Respimat®) according to PASAPQ (Part 2) three-months after the switch**

Estimand:

A. Population: Is defined through inclusion/exclusion criteria of the study protocol to reflect the target population.

B. Variable: Binary variable response.

C. Intercurrent Event (IE): Include death, drop-out due to any adverse event (AE) and treatment discontinuation. For patients experiencing an IE, the most extreme unfavourable value will be assigned (Preference of Spiriva Handihaler®)

D. Population level summary: Proportion of patients preferring Spiriva® Handihaler® and proportion of preferring Spiolto® Respimat®.

Estimand will be assessed by summary statistics.

11.2.2.8 Mean score of willingness to continue with inhaler (Spiolto® Respimat®) according to PASAPQ (Part 2) three-months after the switch.

Estimand:

A. Population: Is defined through inclusion/exclusion criteria of the study protocol to reflect the target population.

B. Variable: Continuous variable response.

C. Intercurrent Event (IE): Include death, drop-out due to any adverse event (AE) and treatment discontinuation. For patients experiencing an IE, the most extreme unfavourable value will be assigned (Willingness to continue equals to 0)

D. Population level summary: Mean score of willingness to continue with the inhaler Spiolto® Respimat®.

Estimand will be assessed by summary statistics.

11.2.2.9 Mean change of patients' dyspnea status according to the mMRC scale within three-months after the switch.

Estimand:

A. Population: Is defined through inclusion/exclusion criteria of the study protocol to reflect the target population.

B. Variable: Continuous variable response.

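### SAP 10.3 allows in-range outcome scores to be deleted or replaced because of their effect on the result, and does not visibly exempt the worst-case values assigned under SAP 11.2

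*SAP*

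**What the plan says.** SAP 10.3 names a Z-score method, without a cut-off, and an IQR method. The IQR method calls a primary or secondary continuous value an outlier when it lies outside Q1 - 1.5×IQR to Q3 + 1.5×IQR. The section continues: "If the effect of the outliers is strong, delete or replace will be examined". Its one visible control is "Any removal or replace at the analysis will be documented, stating the site and patient number as well as the reason for removal". Table 17.10 in Annex 1 lists patient, variable, value, visit and procedure taken.

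SAP 5.1 sends one class of missing data elsewhere: "Missing values due to Intercurrent Event (IE) are taken care at the estimands definitions". For the primary outcome, SAP 11.2.1.1 then states: "For patients experiencing an IE, the most extreme unfavourable value will be assigned (CAT score at 3 Months equals to 40". The secondary estimands assign the matching extremes:

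- EQ VAS (11.2.2.2): "EQ-VAS equals to 0"
- PASAPQ items 1 to 13 (11.2.2.5): "Total score equals to 13"
- PASAPQ Question 14 (11.2.2.6): "Score of Question 14 equals to 1"
- willingness to continue (11.2.2.8): 0
- mMRC (11.2.2.9): 4

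The primary model is described as follows: "Mixed model for repeated measurements (MMRM) assuming random missingness will be fitted".

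The visible protocol text (Section 9.7) asks that removals be documented but has no outlier rule. The visible part of SAP 5.1 does not list one as a change.

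**The concern.** There are two problems.

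**The trigger.** Whether a value stays depends on how far it moves the result, not on whether it is wrong. The questionnaires have fixed ranges and the eCRF checks plausible ranges at entry (SAP 12), so most flagged scores will be in range and can be true answers. With no definition of a strong effect and no stated replacement value, the decision can be taken after the estimate is seen.

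**The assigned values.** Scale extremes are what a fence tends to catch. If a 40 assigned after death or treatment discontinuation is deleted, Month 3 becomes missing, and the MMRM treats it as missing at random. That patient no longer counts as a worst outcome, which is what the primary estimand requires. Only unfavourable values are assigned, so their removal can only move the result in the favourable direction. The study has no control group in which a similar shift would offset it.

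**Working it through.** **Yardstick from the plan.** Protocol 9.5 expects a mean CAT difference of 1.0 and an SD of differences of 9.0, and wants a 95% CI half-width of at most 0.5 with 90% probability. The smallest n with P(t(0.975, n-1)·S/√n ≤ 0.5) ≥ 0.90 at σ = 9 is 1310 (probability 0.9007), which reproduces the stated figure.

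**How many correct values the fence flags.** For normal data the fence is at 0.6745 + 1.5 × 2 × 0.6745 = 2.70 SD from the mean. The two tails hold 0.70%, or 0.0070 × 1310 ≈ 9 correct values.

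**Short scales.** SAP 11.2 labels mMRC and Question 14 as continuous, so 10.3 covers them. With assumed quartiles:

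- mMRC with Q1 = 1 and Q3 = 2: fences 1 - 1.5 = -0.5 and 2 + 1.5 = 3.5, so every true grade 4 is flagged.
- Question 14 with Q1 = 6 and Q3 = 7: lower fence 6 - 1.5 = 4.5, so the neutral and all dissatisfied answers are flagged.

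**Assigned CAT values, by hand.** The documents give no CAT mean, CAT SD or event rate. Assume baseline mean 15, SD 7, true change -1 and 5% events, with 40 assigned first and the Month 3 score fenced afterwards.

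- Month 3 mean = 0.95 × 14 + 0.05 × 40 = 15.3, so the change is 15.3 - 15 = +0.30. Without the 40s it is -1.
- Q1 is at z(0.25/0.95) = -0.634: 14 - 0.634 × 7 = 9.56. Q3 is at z(0.75/0.95) = 0.805: 14 + 0.805 × 7 = 19.63.
- Upper fence = 19.63 + 1.5 × (19.63 - 9.56) ≈ 34.7, so every 40 is flagged.

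**By simulation.** 2,000 samples of n = 1310, scores rounded and held to 0-40, SD of change 9 (correlation 1 - 81/(2 × 49) = 0.17 at SD 7), values on or beyond the fence treated as outliers:

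| Handling | Mean change |
|---|---|
| All data | +0.32 (CI half-width 0.57) |
| Flagged values deleted | -1.02 (0.49) |
| Deleted, two-visit MMRM without covariates | -1.03 |
| Flagged values set to the fence (about 35) | +0.06 |

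A separate simulation with 1500 patients and within-patient correlation 0.5 gives +0.33 and -0.99.

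**When the 40s are flagged.** Percentage of samples, by assumed baseline mean/SD:

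| Events | 15/7 | 15/8 | 18/7 | 18/8 | 22/7 | 22/8 |
|---|---|---|---|---|---|---|
| 5% | 98-100 | 98-100 | 98-100 | 52 | 16 | 0 |
| 10% | 100 | 47 | 22 | 0 | 0 | 0 |
| 15% | 72 | 0 | 0 | 0 | 0 | 0 |

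The 15% row borrows the Protocol 9.5 dropout rate and is an upper case, because not every dropout is an intercurrent event. At SD 9 and 5% events the rate is 22% at mean 15 and 0% at mean 18 and above. At SD 9 with 10% or 15% events it is 0% at every mean tried.

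**Other readings.** If the change score is fenced, about half of the assigned values are flagged in the 15/7, 5% case, and deletion moves +0.33 to -0.39. If only observed scores are fenced, before assignment, the shift is 0.00 to 0.02.

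**The case against.** The strongest reply is that 10.3 is a data-cleaning section. It stands before the analysis sets and estimands and speaks of an observation. A CAT of 40 assigned after death is a scoring rule, and a specific instruction to assign it should prevail over a general clause that only says deletion will be examined. On that reading the CAT effect is negligible. This is a fair and perhaps more natural reading. But the section also speaks of removal or replacement at the analysis, and nothing fixes the order, so the other reading is open too.

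Other points stand as limits:

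- The wording permits deletion and does not require it.
- Removals must be documented and Table 17.10 would show them. That makes a result-driven choice traceable but does not prevent it.
- Tables 6.1.1, 8.1.1 and 13.1.1 are planned on observed data, though nothing says they are free of the 10.3 rule.
- Redacted text, including the detail in SAP 11.3.1 and the bases of several CAT tables, may hold a safeguard.
- The study is descriptive and tests no hypothesis, so an error rate is not at stake. The reported mean change and its interval are.
- The size depends on assumed inputs and on which quantity is fenced.

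None of this supplies a definition of a strong effect or a requirement that a deleted value be shown to be wrong.

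**Conclusion.** The concern holds on the text. SAP 10.3 allows in-range scores to be removed or replaced because they influence the result, and no visible text protects the values that the SAP 11.2 estimands assign. This should be changed, and confidence in the reading of 10.3 is high.

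The size is less certain. For observed CAT scores it is about zero. The reversal from +0.32 to -1.02 is a shift of 1.34 points, larger than the expected change of 1.0 and more than twice the planned half-width of 0.5. It requires screening after assignment, deletion rather than replacement, a fence on the Month 3 score, and a combination of CAT mean, SD and event share at which 40 lies outside the fence. A change-score fence roughly halves the shift, to 0.72 (from +0.33 to -0.39).

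**What to change.** Replace the delete-or-replace sentence in SAP 10.3 with a rule of this content:

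- Only values out of range, or confirmed as wrong by query, are corrected or set to missing, and this is done before database lock.
- No in-range questionnaire score is deleted or replaced in a primary or secondary analysis.
- Values assigned under the SAP 11.2 estimands are exempt from outlier flagging.
- Values beyond the IQR fences are listed in Table 17.10. Any analysis without them is a labelled sensitivity analysis, shown beside the all-data result.

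The cost is one paragraph of SAP text. The listing shell already exists, no new data are needed, and at most one optional sensitivity run is added. If redacted text already contains such a safeguard, a cross-reference from 10.3 would be enough.
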